# Report of Suspected Child Abuse and Neglect:

If a participant discloses abuse of a child to the research assistant during a research interview, he/she will immediately contact the PI at their site (or co-investigators in her absence) who will facilitate calling the CT Child Protective Services Hotline and writing a written report to be filed within the guidelines for reporting in the State of CT. This would include information about neglect, physical, sexual or psychological abuse of a child. Fathers self-reports of child maltreatment risk behavior will be monitored carefully for evidence of behaviors that reach the level of reportable child abuse. Incidents of yelling or spanking may not rise to the level of a child abuse report based on CT law. Further, CT law does not require reporting of IPV to child protective services, unless the IPV incident described included the child. Men reporting about their past incidents of IPV will not alone trigger a child protective services report. Reports of new incidents of IPV or child maltreatment risk behaviors during the course of the study will be assessed to determine if they meet the child abuse reporting laws outline by CT statute. In all cases of new disclosures of abuse, reports will be filed with protective services. We will provide support to the father following the report through his assigned clinician or through other services available at the PFDP, or in the community. What data are available suggest that sensitive mandated reporting of potential child abuse and neglect does not necessarily threaten the integrity of recruitment or participation

# Suicidal or Homicidal Ideation or Intent:

Upon report of suicidal intentions or the threat of harm to others, the participant will be secured to a higher level of treatment (e.g. hospital setting) while the female participant will be notified for her safety if necessary (e.g., as in a Tarisoff report, if her safety is threatened). Our team has expertise in dealing with high-risk behaviors and abides by all state and federal regulations. If a research assistant learns of homicidal or suicidal ideation or intent, they will immediately contact the PI at their site who will assess the participant and facilitate a higher level of care if needed. Drs. [name] are licensed clinical psychologists in the state of CT as are Drs. [name], [name]

9. Waiver of Consent/Documentation of Consent: In certain circumstances, the IRB may grant a waiver of documentation of consent, or a full waiver of consent, depending on the study. If you will request either a waiver of consent, or a waiver of signed consent for this study, complete the appropriate section below.

# □Not Requesting any consent waivers

# □ Requesting a waiver of signed consent (e.g., verbal or online consent only):

Recruitment/Screening only (if for recruitment, the questions in the box below will apply to recruitment activities only)
 Entire Study (Note that an information sheet may be required.)

# For a waiver of signed consent, address the following:

- Would the signed consent form be the only record linking the subject and the research? YES ⊠ NO
- Does a breach of confidentiality constitute the principal risk to subjects? YES oxtimes NO  $\Box$

# OR

- Does the research pose greater than minimal risk? YES  $\Box$  NO  $\Box$
- Does the research include any activities that would require signed consent in a non-research context?
   YES □ NO □

# □ Requesting a waiver of consent (if you are not obtaining ANY consent):

Recruitment/Screening only (if for recruitment, the questions in the box below will apply to recruitment activities only)

# □ Entire Study

For a waiver of consent, please address all of the following:

- Does the research pose greater than minimal risk to subjects?
   Yes If you answered yes, stop. A waiver cannot be granted.
   No
- Will the waiver adversely affect subjects' rights and welfare? YES □ NO⊠
- Why would the research be impracticable to conduct without the waiver? Conducting a full informed consent on any possible participant who comes into the PDFP without assessing their eligibility will put undue burden on clinic and study staff and participants. Informed consent for this study will take time to ensure clients understand procedures and to complete the informed consent quiz. Doing this with ineligible clients is burdensome for all involved and may be annoying for clients who are then ineligible.
- Where appropriate, how will pertinent information be returned to, or shared with subjects at a later date? If the father is not eligible based on screening due to severe IPV that involves hospitalization or strangulation, or a current full protective order related to his child, he will be informed that he does not meet our demographic criteria based on his initial screening. No mention of contact will mother will be made. The study team will retain de-identified information about clients screened and reason for ineligibility for Consort Diagram purposes but no information about individual clients will be retained. Screening forms will be shredded as soon as fathers are notified of their ineligibility or if they decline participation in the study following informed consent.

# **10. Assessment of Current Health Provider Relationship for HIPAA Consideration:**

Does the Investigator or any member of the research team have a direct existing clinical relationship with any potential subject?

 $\Box$ Yes, all subjects

 $\Box$  Yes, some of the subjects

 $\boxtimes No$ 

If yes, describe the nature of this relationship. Write here

**11. Request for waiver of HIPAA authorization:** (When requesting a waiver of HIPAA Authorization for either the entire study, or for recruitment purposes only. Note: if you are collecting PHI as part of a phone or email screen, you must request a HIPAA waiver for recruitment purposes.)

# **Choose one:**

 $\Box$  For entire study

☑ For recruitment/screening purposes only

□ For inclusion of non-English speaking subject if short form is being used and there is no translated HIPAA research authorization form available on the University's HIPAA website at hipaa.yale.edu.

i. Describe why it would be impracticable to obtain the subject's authorization for use/disclosure of this data: We will be contacting participants by phone to provide

information about the study and screen for eligibility. Conducting full HIPAA authorization to ask clients screening questions would be impractical to conduct and collect during the screening process.

ii. If requesting a waiver of **signed** authorization, describe why it would be impracticable to obtain the subject's signed authorization for use/disclosure of this data: *Write here* 

The investigator assures that the protected health information for which a Waiver of Authorization has been requested will not be reused or disclosed to any person or entity other than those listed in this application, except as required by law, for authorized oversight of this research study, or as specifically approved for use in another study by an IRB.

Researchers are reminded that unauthorized disclosures of PHI to individuals outside of the Yale HIPAA-Covered entity must be accounted for in the "accounting for disclosures log", by subject name, purpose, date, recipients, and a description of information provided. Logs are to be forwarded to the Deputy HIPAA Privacy Officer.

# SECTION VI: PROTECTION OF RESEARCH PARTICIPANTS

1. Confidentiality & Security of Data: Describe the steps that will be taken to secure the data during storage, use and transmission as outlined in the below sections. NOTE: Data can include paper files, data on the internet or websites, computer files, audio/video files, photographs, etc. and should be considered in the responses to the below sections.

Confidentiality with regard to completed research forms will be maintained via a numbered reference system maintained by the PI and Project Directors. Participants' names will appear only on the consent form, HIPPA authorization form, and "key" form in a password protected file only assessable by the PI. All data will be identified by participant ID only. All measures, video and recordings will be labeled by participant ID only. Subjects who decline participation in the study or those who wish to withdraw from the study can continue in their treatment at the outpatient facilities as they would if they were not approached to participate in a study. As stated above to further protect against potential risks to confidentiality for this population, a Certificate of Confidentiality will be obtained. Participants will clearly be informed of the limits of this confidentiality, which are in cases of suspected child abuse or neglect, and imminent risk for harm to self or others (particularly intimate partner or child).

Therapy sessions will be video recorded to ensure that the therapists administer the study treatments within manual guidelines and are engaging the intervention targets of emotion regulation and reflective functioning. To assure the confidentiality and protection of participants with respect to video and audio recording, the following steps will be taken:

- Participants have the right to refuse recording. Participants who consent to recording will be informed that they have the right to stop at any time during any session.
- Each therapist will conduct the recording him/herself. All recording will take place in the treatment facility in private offices.
- During treatment sessions the therapist's behavior is of primary interest for process assessment, the camera will be directed at the therapist.

- Each digital recording will be labeled with the participant's study identification number and a coded session date.
- The therapist or RA will then store the digital recording on a password protected server. Yale utilizes a HIPAA compliant, encrypted and fire wall protected server called One Drive. Once the files are uploaded onto the One Drive server, the session will be deleted from the video camera data cards.
- Access to the recordings will be limited to specially trained research raters who will rate the tapes according to established process rating systems. All ratings will be done in esearch offices at Yale, UCONN or U of Delaware.
- Upon completion of these ratings, the recordings will be deleted.

Aside from video recordings of sessions, all other study data will be de-identified and stored within the REDCap database. Consent forms and releases of information for the study will be kept in a secure file on a password protected computer.

The treatments provided could be an option for mandated treatment. If clients wish their study therapist to provide information to court support services or some other entity related to their participation in treatment, the study therapist and/or PI will do so with a signed release from the client. A form letter will be created that indicates the dates of program attendance, nature of the treatment being provided and completion of treatment. No information about the research data collected or study components will be provided only their attendance and successful or unsuccessful completion of treatment. If a client wishes for other information to be disclosed, they can indicate this on the release form.

Criminal and child protection records will be collected by providing an excel sheet with participant names and dates of birth to the Court Support Services Division of the State of CT and the Department of Children and Families along with signed releases of information from participants to provide their names to the agency to provide data to us. We will provide no other information to DCF or CSSD about the participants. Data will be entered into the excel sheets by CSSD or DCF staff and returned to the project director. These will be transferred from the agency to the project director using secure data transfer (OneDrive).

2. What participant information will you be collecting? Describe the identifiers that will be included or associated with the data and/or specimens (e.g., names, addresses, telephone/fax numbers, email addresses, dates (date of birth, admission/discharge dates, etc.), medical record numbers, social security numbers, health plan beneficiary numbers, etc.)

We will collect names, birth dates, criminal records, Department of Children and Families records and contact information (phone numbers, addresses and email addresses) from study participants. If a participant drops out of the research study we will make efforts to retain them in the study for intent to treat analysis. This information will be kept with the signed informed consent in a locked cabinet in the PI's office. It will not be linked to study measures which will be locked in another office space under the participants study ID number.

Other potentially identifying information to be collected:

⊠Audiotapes

⊠Videotapes

□Faces (focus groups, photographs or other way that an individual would be physically recognized)

Potential for identification from the bulk of the information, even if direct identifiers are not collected (deductive disclosure).

3. How will the research data be collected and recorded?

Data will be collected via interview and entered directly into an on-line REDCap data system. REDCap is an on-line, secure data capture. Responses to the PDI will be recorded via audio recorders. They will be downloaded onto a secure password protected servers that only study team members will have access. Digital recordings will be conducted by the therapist and stored on a HIPAA secure server. They will be rated by trained therapy fidelity coders. All data will be stored on a password protected and encrypted HIPAA compliant server at the Yale School of Medicine and entered on a secure REDCap database.

Collection of records from DCF and criminal records: Fathers will sign a release of information for collection of data from DCF related to his arrests for family violence related incidents and reports of IPV and child maltreatment to DCF. An excel spread sheet will be created that will include the names of study participants and their dates of birth. These will be sent to the contact person at DCF who will search records via a secure data transfer (encrypted and firewall protected using Yale's secure file transfer). The contact person who will be a state employee with approved access to the DCF and state arrest databases will search the names and dates of birth. The state employee will fill in the excel spread sheet with the data requested (number of reports to DCF for IPV and CM over the 26 weeks of treatment and number of IPV or CM related arrests over the 26 weeks of treatment). If an incident appears in both databases this will be noted to prevent double counting of a single incident of IPV multiple times due to reporting to both the police and DCF. The completed dataset will be returned to [name] via the same Yale secure file transfer. DCF will not keep any records of this data once transferred back to [name]. The excel sheet will then be updated by [name] with participant study ID numbers and the names and dates of birth will be deleted from the file. This ID only dataset will be saved for merging with other study data for analysis. This will ensure that arrest and DCF data will not be attached to participant names once it returns to Yale. The data will be stored on a password protected server only assessible by the study team.

4. If identifiers will be associated with the data and/or specimens, describe whether a record or list containing a code (i.e., code number, pseudonyms) will be used, where the list will be stored, who will have access to the list and when it will be destroyed.

The only file that will link the study participants to their study ID number will be an excel file kept on a password protected and encrypted computer in the PI's research lab. Only the PI and study RAs will have access to this file.

5. Describe where, how and for how long the data (hardcopy (paper) and/or electronic data) and/or specimens will be stored. Study data will be retained for 10 years from study completion to allow for analysis and use of data to answer research questions and the development of F4C. Video and Audio recordings of fathers sessions will be destroyed based on their wishes at the time of consent. If fathers will allow us to retrain their videos for training or research, these will be kept indefinitely. Using these videos for training purposes has been useful previously to train clinicians. Fathers will be reminded that their videos will be kept indefinitely at the time of recording. The fathers will not be identified in the videos as IPV offenders. They appear as fathers interacting with their children only. If fathers want their video and audio recordings deleted at the completion of the study, these will be

deleted from all servers following fidelity coding of session videos/supervision and following transcription of audio files for analysis.

All portable devices must contain encryption software, per University Policy 5100. If there is a technical reason a device cannot be encrypted please submit an exception request to the Information Security, Policy and Compliance Office by clicking on url http://its.yale.edu/egrc or email [contact]

6. Identify who will have access to the data and/or specimens. If the data and/or specimens will be transferred to and/or from outside collaborators, identify the collaborator to whom the data and/or specimens will be transferred and how the data and/or specimens will be transferred. Only study team members will have access to the data. [name] will have access to video recorded sessions stored on a One Drive folder. They will oversee trained coders who will rate therapy sessions for focus on emotion regulation and reflective functioning important to the intervention. They will access recordings on this server. They will not be removed from this server at any time nor shared with others via download. [name] has received IRB exemption from her university IRB for this work. Letters to this regard are uploaded with this protocol.

7. What will be done with the data when the research is completed? Are there plans to destroy the identifiable data or the link to personal identifiers? If yes, describe how, by whom and when identifiers will be destroyed. If no, describe how the data and/or identifiers will be secured. The data will be stored in a de-identified dataset on the Yale secure server. Only Drs. [name], their research team will have access to the data. No personal identifiers will be retained.

8. Will a Certificate of Confidentiality be needed? (*See also the NIH Certificate of Confidentiality Kiosk,* http://grants.nih.gov/grants/policy/coc/index.htm) Yes a certificate of confidentiality will be attained from NICHD which is now standard for studies that involve collection of information that participants may not want disclosed to the court.

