The RA will complete study assessments in person or via zoom with fathers, mothers and partners at baseline, immediately following intervention completion, at 6 and 12 month follow-ups. Each measure and timing of assessment are outlined in Table 1.

Table 1. Assessment	Rater	Baseline	Weekly During	Monthly During	Post- intervention	6& 12 Month- FU
Schedule			Intervention	Intervention		_
ir v Out comes						
Family Socialization Interview Revised (FSI-R)  – IPV module	Masked Coder	X			X	Х
Time-line follow-back for IPV (56, 57)	Father, Mother, Current Intimate Partner		Х			
Abusive Behavior Inventory (ABI)	Father, Mother, Current Intimate Partner	X			X	X
Court and Arrest Records	N/A	X				Х
Child Maltreatment and Parenting Outcomes						
Child Protective Services Records	N/A	X				X
Family Socialization Interview Revised (FSI-R)  – Parenting Risk module	Masked Coder	x			X	X
Timeline Followback-CM Risk	Father and Mother		х			
Conflict Tactics Scale-Parent Child	Father and Mother	x			x	X
Father-Child Free Play coded using Child Interactive Behavior Rating (CIB)+	Masked Coders	X			X	X (12 month only)
Children's Emotions Scale (RCES)	Mother and Father					
Brief Infant Toddler Social Emotional Assessment (BITSEA) Trauma Symptom Checklist for Young Children (TSCYC) or Trauma symptom checklist for children (TSCC) appropriate for child age	Mother and Father Children >7-Self Report	X			X	X
Kiddie Diagnostic Interview Schedule PTSD Module OR Diagnostic Infant and Preschool Assessment (DIPA) modified PTSD module	Mother and Father	X			x	x
Satisfaction Outcomes						
Client Satisfaction Questionnaire 8 (58)	Father				Х	
Intervention Targets (Mechanisms)						
Unified Protocol Skill Use Scale (UPSUS)122 and select items from the 28-item Brief COPE	Father		X			
Difficulties in Emotion Regulation Scale (59) DERS Short Form	Father	X	Х		x	Х
Reflective Functioning Questionnaire-8 (RFQ)(60)	Father	X	Х			
Parent Reflective Function Questionnaire (PRFQ) (61)	Father	X	X			
Intervention Process Variables						
Working Alliance Inventory (62)	Father and Clinician			Х		
CHANGE Coding	Trained Reliable Coders			Х		
Motivation to Change	Father			Х		

	1			1	1
Therapist Session Report Form	Clinician		x		
Other variables to classify the sample					
STRESS Trauma History and PTSD Scale	Father	Х			
Alcohol Use Disorders identification Test (AUDIT) – Self report(66)	Father	Х			
Drug Abuse Screening Test- 10 (DAST- 10)(67)	Father	Х			

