# Treatment Phase.

Each treatment will be delivered weekly over 18 weeks. Male participants will meet online or be contacted via phone weekly with the RA to complete self-report assessments of IPV behaviors, father-child interactions and *substance use*. The RAs will be blind to the participants' treatment conditions. Study therapists will complete weekly session reports of session content and skill acquisitions based on completed homework.

*Fathers for Change*: F4C focuses on: 1) the fathering role to facilitate engagement, 2) RF to understand self, partner and children and emotion regulation skills to reduce IPV and child maltreatment F4C focuses on understanding of emotional experiences, how they impact thinking and behaviors related to partners, co-parents and children. F4C clients will meet individually with their F4C therapist for 50 minutes per week over 18 weeks.

**Batterer Intervention Program:** The BIP is a psychoeducational intervention that will be delivered in 50- minute individual sessions over 18 weeks. The intervention focuses on the impact of violence on victims, power and control tactics, and societal influences supporting men's violence toward women. The intervention includes didactics and experiential exercises including role plays to teach management skills. anger BIP is typically delivered in a group format, however will also be adapted to an individual Therapies will be delivered either in person or via format as part of the current study. secure/password protected zoom virtual sessions. All Yale safety protocols with regard to COVID-19 will be followed.

**Therapist Training.** Master's level clinicians will be trained to deliver the study interventions. [name] will utilize the therapist training manual, slides and videos generated from her pilot studies to train F4C therapists. She will meet weekly with F4C therapists for supervision. BIP-I and BIP-G therapists will be trained by [name] using the BIP manual and training materials modified for individual treatment delivery. BIP clinicians will meet weekly with [name] for supervision and intervention adherence.

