# SECTION VIII: RESEARCH ALTERNATIVES AND ECONOMIC CONSIDERATIONS

1. **Alternatives:** What other alternatives, if any, are available to the study participants outside of the research?

Participants will be able to receive intervention as usual offered at the Parent and Family Development Program if they do not want to participate in research.

2. **Payments for Participation (Economic Considerations):** Describe payments that will be made to participants, if any, the amount and timing of payments, and the conditions for receiving this compensation (if applicable). If you plan to hold a drawing, be sure to include the following on any consent or recruitment materials mentioning the lottery: 1) the value of the prize; 2) the sponsor of the prize (this cannot be a federal funding source); 3) the odds of winning; and 4) that there are no restrictions to winning.

Fathers and coparents will be paid \$50 for their completion of baseline assessments. Children younger than 7 will receive a small toy (worth \$5-10) for completing play assessments. All children in a family within the age range will be offered the toy to prevent any conflict within the family. Children over 7 will receive \$20 for completing play assessments and symptom questionnaires.

During Treatment: Fathers and coparentswill receive \$5 for each completed weekly log over the 18 weeks of treatment.

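### The one records request with a stated period (26 weeks of treatment) contradicts the 18-week treatment text and does not deliver Table 1's baseline, 6-month and 12-month records

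*Combined protocol and SAP*

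**What the plan says.** **Records request.** Section VI, item 3 has a state employee search the DCF and arrest databases and enter the "number of reports to DCF for IPV and CM over the 26 weeks of treatment and number of IPV or CM related arrests", with arrests counted over the same 26 weeks. The paragraph names no phase. Section VI, item 1 describes a similar request to the Court Support Services Division (CSSD) and DCF. It states no period and no variable, and it limits what the agencies learn about participants to names, birth dates and signed releases.

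**Schedule.** The Baseline assessments section says: "Each measure and timing of assessment are outlined in Table 1". In that table the rows "Court and Arrest Records" and "Child Protective Services Records" are marked at baseline and in the 6- and 12-month column, and nowhere else. The Follow-up section counts those months from the end of the intervention.

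**Treatment length.** The Treatment Phase section says "Each treatment will be delivered weekly over 18 weeks". The payment text in Section VIII pays fathers and coparents "for each completed weekly log over the 18 weeks of treatment". Eighteen weeks also appears in the Phase I aims (aim 4, hypothesis ii), in Phase II Aim 2, and as 18 weekly sessions in the randomization text. The only other place that gives 26 weeks is the background description of F4C in Section IV, item 2.

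**Use of the records.** The Child Maltreatment Risk paragraph calls the FSI-R the primary outcome measure and says its rating combines self-report, collateral reports and records.

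**The concern.** Two conflicts meet in one sentence. The counting window is tied to a treatment length that most of the document does not use. Whichever length applies, a treatment-period count is not what Table 1 schedules, because Table 1 wants records at baseline and at two points after treatment.

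Family violence at the 6- and 12-month follow-ups is part of Phase II hypothesis 1a. Records are the one FSI-R input that does not depend on what a father, mother or partner tells the study. If the request went out as worded, masked coders would rate follow-up mostly without them.

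The request also names only counts; whether dates would come back is not stated. A count that spans the end of treatment cannot be divided afterwards without dates. Nor does the document say how an agency that holds only a name and birth date would know when a given father's treatment began.

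**Working it through.** **1. Can the 26 weeks be reproduced?** Inputs: 18 sessions, one per week (randomization text); follow-up at 3 months in Phase I (Phase I aims) and at 6 and 12 months in Phase II (Follow-up section). Assumption: 3, 6 and 12 months are 13, 26 and 52 weeks.

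- Treatment alone: 18 × 1 = 18 weeks
- Treatment plus 3 months: 18 + 13 = 31 weeks
- Treatment plus 6 months: 18 + 26 = 44 weeks
- Treatment plus 12 months: 18 + 52 = 70 weeks

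None gives 26. The 6-month post-treatment interval alone is 26 weeks, but the request ties its weeks to treatment.

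**2. What does the request cover in Phase II?** Take it literally, with 18-week treatment and a 26-week window opening at treatment start.

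| Quantity | Calculation | Result |
|---|---|---|
| Pre-baseline weeks requested | window opens at treatment start | 0 |
| Post-intervention weeks covered | 26 − 18 | 8 of 52 (15%) |
| of which in months 0 to 6 | 8/26 | 31% |
| of which in months 6 to 12 | 0/26 | 0% |
| Weeks to the 12-month visit left uncounted | 70 − 26 = 44; 44/70 | 63% |
| Make-up of the single count | 18 treatment + 8 follow-up | 69% and 31% of the window |

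If treatment did last 26 weeks, the post-intervention cover would be 26 − 26 = 0 of 52 weeks. Eight weeks is therefore the most that the wording yields.

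**3. Against Table 1.** The baseline cell is empty because nothing before treatment is requested. The 12-month cell has no data from months 6 to 12. The 6-month cell has at most 8 follow-up weeks, and these are merged with treatment weeks. No scheduled cell is filled.

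**4. Does Section VI, item 1 fill the gap?** It gives no period and no variable, so it does not. It also differs from item 3 on logistics:

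- Item 1: CSSD and DCF staff complete the sheets, which return through OneDrive.
- Item 3: a single DCF contact searches both databases, and the file returns through Yale's secure file transfer. The flag that stops one incident being counted twice depends on someone seeing both databases, which item 1 does not provide for.

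**The case against.** The best defence is that item 3 sits in a data-security section and may be leftover Phase I text. The same item describes recording the PDI, which appears in the Phase I analysis but not in Table 1. Table 1 is the stated authority on timing, and item 1 may be the request meant for Phase II. This stands in part. The phase is not stated, and a reader might infer that item 3 is the only records request and that Phase II has none; item 1 rules out that wording. The defence does not remove the conflict. Phase I treatment is also 18 weeks, and a 26-week window would stop 31 − 26 = 5 weeks short of its 3-month follow-up. Phase II would be left with a request that has no period.

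A reader might also infer that nothing on record would be known before baseline. The documents do not support that. Many fathers are referred by DCF because of recent violence or maltreatment risk, and court or police records are one possible source at eligibility screening. Some earlier information may therefore be held, although the request does not ask for it. DCF would also know when it made a referral, but a referral is not a treatment start, and community referrals are allowed.

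A third tempting inference is that the primary outcome is biased. Nothing shows this. Both arms use the same request, and self-report and collateral reports still feed the FSI-R.

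**Conclusion.** The concern holds as an inconsistency that, if carried out as written, would return the wrong data for one of three inputs to the FSI-R child-maltreatment rating. The figures are calendar coverage only: 8 of 52 post-intervention weeks counted at most, and 44 of 70 weeks to the 12-month visit uncounted with 18-week treatment. They rest on three assumptions: the sentence is used unchanged in Phase II, the window opens at treatment start, and no dates are returned with the counts. No loss of power and no difference between arms has been calculated or shown.

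This should be corrected. Confidence is medium, because actual practice may be wider than the text. The review takes no position on whether 18 or 26 weeks is right.

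**What to change.** 1. Reconcile the F4C background description, the Treatment Phase section and Section VI, items 1 and 3, on treatment length. State which phase each records request serves, which agencies answer it and by which transfer route.
2. Reword the request to Table 1: a pre-baseline look-back whose length the sponsor sets, and intervals ending at the 6- and 12-month follow-ups, with treatment separable from follow-up.
3. Choose how to achieve this. One way is to ask for incident dates and have staff masked to arm assign them to intervals at the site. The other is to keep counts and state how each father's window reaches the agencies within item 1's limit on what they are told.
4. State when the pulls are made, so that records are in hand for each FSI-R rating. As Table 1 reads, the FSI-R is also rated post-intervention, where no records are marked.
5. Say who applies the duplicate flag if two agencies complete the sheets.

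The cost is a revised data request and the reconciliation of two descriptions. Dated incidents are more identifying than counts, so the release and IRB wording should be checked to confirm that they cover the period and the dates. A reader might infer that fathers already enrolled must sign again. The release as described in item 3 carries no time limit, so that is not established.
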